7 STUDY POPULATION

The study population is individuals infected with SARS-CoV-2 who have symptoms associated with COVID-19 that is either not under active medical treatment or is being treated as an outpatient. Study subjects must be symptomatic for 3 days or less and have a positive COVID-19 antigen test using an FDA authorized SARS-CoV-2 antigen diagnostic test at or within the past 24 hours of screening. Study subjects will be randomized to treatment arm within dose in a 2:1 ratio according to a fixed schedule using a permuted block design. The targeted number of subjects randomized per dose is 30 (20 volunteers to the RD-X19 arm, 10 subjects to the sham arm). This is a sample size of convenience as this is a hypothesis generating study.

The target population should reflect the subject population with uncomplicated COVID-19 in the community at large.

Subject Inclusion and Exclusion Criteria must be confirmed by a study clinician, licensed to make medical diagnoses.

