8.5.3 Investigator Decision to Discontinue Subject Use of Device

A subject may be removed from the study for the following reasons post initial device use; however, whenever possible the subject should be followed for safety evaluations per protocol:

- Study non-compliance to protocol requirements that in the opinion of the participating clinical site PI or appropriate sub-investigator poses an increased risk (e.g., missing safety labs) or compromises the validity of the data.
- Lost to follow-up. (A subject will be considered lost to follow-up if he or she fails to appear for a follow-up assessment. Extensive effort (i.e., generally three documented contact attempts via telephone calls, e-mail, etc., made on separate occasions) will be

made to locate or recall the subject, or at least to determine the subject's health status. These efforts will be documented in the subject's study file.)

- Medical disease or condition, or new clinical finding(s) for which continued participation, in the opinion of the participating clinical site PI or appropriate sub-investigator, might compromise the safety of the subject, interfere with the subject's successful completion of this study, or interfere with the evaluation of safety.
- If any AE, clinical laboratory abnormality or situation occurs such that continued participation in the study would not be in the best interest of the subject.
- The occurrence of a SAE.
- If the subject is using the device in any manner inconsistent with instructions and protocol directives and procedures.

If the subject agrees, every attempt will be made to follow all AEs through resolution or stabilization.

Subjects who withdraw or are lost to follow-up after signing the informed consent form (ICF) and use of the RD-X19 device will not be replaced. Subjects who withdraw or are withdrawn from this study after signing the ICF but before use of the device may be replaced.

The reason for subject discontinuation or withdrawal from the study will be recorded on the appropriate e-CRF.

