8.5.4 Follow-up of Study Subjects Who Discontinue Device Use

Discontinuation of study device use does not constitute discontinuation from the study, and the study procedures for early termination should be completed as indicated by the Study Schedule of Activities. If a clinically significant finding is identified, including, but not limited to, changes from baseline, after enrollment, the participating clinical trial site PI or qualified designee will determine if any change in subject management is needed. Any new clinically relevant finding will be reported as an AE.

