9 STUDY ASSESSMENTS AND PROCEDURES

9.1 Screening Assessments

9.1.1 Screening Procedures

At the screening visit, and prior to any other study-related activities, the participating clinical site PI or appropriate sub-investigator will provide the subject with detailed study information and will obtain written informed consent (see section 11.1.1 for more details).

Subject numbers will be assigned with the three-digit numerical site number beginning with numbers greater than one hundred (e.g. 101) followed by an alphanumeric cohort identifier (e.g. C1) and finally a two digit unique numerical identifier assigned with each new subject (e.g. 01).

Example Subject Number: 101-C1-01

COVID-19 Screening

Eligible subjects presenting with uncomplicated COVID-19 must have an oral temperature of at least 100 °F or have at least two moderate or severe symptoms (cough, nasal congestion, or sore throat, headache, chills/sweats, muscle or joint pain, fatigue, or nausea) and consent to be randomized within 3 days of first symptom onset. The subjects will self-assess their COVID-19 symptoms as none (0), mild (1), moderate (2), or severe (3) during screening.

Additionally, subjects who identify with symptomatology associated with COVID-19 will be screened by taking a nasal culture and analyzed for the presence of SARS-CoV-2 by an FDA authorized SARS-CoV-2 antigen test (e.g. BD Veritor™ Plus System, AccessBio Carestart). These systems allow for rapid detection of SARS-CoV-2 via immunoassay for the direct and qualitative detection of SARS-CoV-2 antigens. Subjects presenting at the time of screening that have tested positive via a SARS-CoV-2 rapid antigen test within the past 24 hours and can provide documentation confirming proper identification, the date of the test and testing location, positivity of the result, and name/identity of the assay used to generate the result, are also eligible for enrollment.

There is a small amount of risk to subjects who report mild-to-moderate symptomatology consistent with COVID-19 may have an unknown health problem or co-morbidity at the time of screening that can lead to worsening of condition or hospitalization during study.

General Screening

Some or all of the following assessments are performed during the screening visit to determine eligibility requirements as specified in the inclusion and exclusion criteria:

- Obtain medical history focusing on conditions per protocol exclusion criteria.

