9.3.1 Efficacy assessments

Various endpoints will explore the impact of RD-X19 treatment on the reduction in log10 SARS-CoV-2 viral load and alleviation of symptoms associated with COVID-19. Both the magnitude of reduction as a function of dose as well as time to clearance will be assessed in support of the primary efficacy analysis. Subjects will be instructed to fill out a diary card or electronic equivalent to assess their signs and symptoms of disease twice daily. Each of the eight symptoms will be rated on a scale from none (0) to severe (3).

- Time weighted average change in viral load from baseline by RT-qPCR from Day 1 to Day 8
- Geometric mean viral load as measured in saliva on day 1, 3, 5, and 8 by RT-qPCR
- Proportion of subjects demonstrating viral load reduction $\geq 95\%$ by RT-qPCR (at each visit)
- Time to undetectable viral load in saliva by RT-qPCR.
- Proportion of subjects demonstrating clearance of viral infection, defined as a negative test via RT-qPCR on Day 8/ET.
- Median time to alleviation of symptoms,
 - The time to alleviation of symptoms endpoint, is defined as the time when all eight symptoms (cough, sore throat, nasal congestion, headache, chills/sweats, muscle or joint pain, fatigue, and nausea) had been assessed by the subject as none or mild.
- Change in COVID-19 Severity Score from baseline
 - The COVID-19 Severity Score is defined as the sum of all the individual symptom severity scores divided by the total number of symptoms assessed (8).
- Viral load by viral titer (at each visit)

- The paired oropharyngeal swab and saliva sample from each subject at each visit allows for independent analysis via two different live virus sampling methodologies and also a direct paired sample comparison of the viral load present in the back of the throat versus saliva.

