5.5.2 Analysis of Secondary Efficacy Endpoints

The following 6 secondary efficacy endpoints will be summarized using descriptive statistics by visit, as appropriate:

- log10-transformed Viral load as measured in saliva by RT-qPCR at each visit by RT-qPCR
- proportion of subjects with $\geq 95\%$ reduction in SARS-CoV-2 viral load by RT-qPCR at each visit
- time to clearance of viral infection in saliva via RT-qPCR
- proportion of subjects demonstrating clearance of viral infection via RT-qPCR at Day 8/ET visit
- COVID-19 composite severity score at each visit
- time to alleviation of COVID-19 symptoms, defined as the number of hours from the first dose to the first time when all eight symptoms had been assessed by the subject as none (0) or mild (1)
- time to sustained alleviation of COVID-19 symptoms, defined the number of hours from the first dose to the time when all eight symptoms had been assessed by the subject as none (0) or mild (1) and no single symptom reoccurs later at a level above mild (1).

Both time to alleviation of COVID-19 symptoms and time to sustained alleviation of COVID-19 symptoms will be derived from self-assessment by study subjects and recorded on the subjects' diary cards.

For log10-transformed viral load data, geometric means will be computed by exponentiating (base 10) the group means of the log10-transformed viral load. Time-to-event variables will be evaluated using the Kaplan-Meier method and p-values for treatment comparison will be provided via log rank test.

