	n (%) Censored	XX (XX.X)	XX (XX.X)	XX (XX.X)
	Median of Time	XX.X	XX.X	XX.X
	25 th , 75 th Percentiles	XX.X, XX.X	XX.X, XX.X	XX.X, XX.X
	95% CI of Median	(XX.X, XX.X)	(XX.X, XX.X)	(XX.X, XX.X)
	P-value RX-X19 vs. Sham	0.XXX	0.XXX	
Per-Protocol	N	XX	XX	XX
	n (%) Censored	XX (XX.X)	XX (XX.X)	XX (XX.X)
	Median of Time	XX.X	XX.X	XX.X
	25 th , 75 th Percentiles	XX.X, XX.X	XX.X, XX.X	XX.X, XX.X
	95% CI of Median	(XX.X, XX.X)	(XX.X, XX.X)	(XX.X, XX.X)
	P-value RX-X19 vs. Sham	0.XXX	0.XXX	

Abbreviation: CI = Confidence Interval

Note 1: Alleviation of COVID-19 symptoms is defined as all eight symptoms assessed by the subject as none (0) or mild (1).

Note 2: Time to alleviation is calculated as the number of hours from the first dose to the time of the first occurrence of symptoms alleviation. Subjects who did not achieve alleviation at the last assessment of study are considered censored at the time of the last assessment.

Note 3: Percentiles and 95% CI of median are derived using the Kaplan-Meier method. P-values for treatment comparison are from Log Rank Test.

Source: Listing 16.2.6.1.2, 16.2.5.3

O:\Studies\EmitBio\EB-P12-01\Biometrics\Programs\Tables\xxx.sas ran on Month Day, Year at hh:mm on data from Month Day, Year.

Figure 15.2.1 - Kaplan-Meier Plot of Time to Alleviation of COVID-19 Symptoms for Intent-to-Treat Population

Figure 15.2.2 - Kaplan-Meier Plot of Time to Alleviation of COVID-19 Symptoms for Per-Protocol Population

Table 14.2.5.2 – Time to Sustained Alleviation of COVID-19 Symptoms

Population	Statistics	4 Days RD-X19	7 Days RD-X19	Sham
Intent-to-Treat	N	XX	XX	XX
	n (%) Censored	XX (XX.X)	XX (XX.X)	XX (XX.X)
	Median of Time	XX.X	XX.X	XX.X
	25 th , 75 th Percentiles	XX.X, XX.X	XX.X, XX.X	XX.X, XX.X
	95% CI of Median	(XX.X, XX.X)	(XX.X, XX.X)	(XX.X, XX.X)
	P-value RX-X19 vs. Sham	0.XXX	0.XXX	
Per-Protocol	N	XX	XX	XX
	n (%) Censored	XX (XX.X)	XX (XX.X)	XX (XX.X)
	Median of Time	XX.X	XX.X	XX.X
	25 th , 75 th Percentiles	XX.X, XX.X	XX.X, XX.X	XX.X, XX.X
	95% CI of Median	(XX.X, XX.X)	(XX.X, XX.X)	(XX.X, XX.X)
	P-value RX-X19 vs. Sham	0.XXX	0.XXX	

Abbreviation: CI = Confidence Interval

Note 1: Sustained alleviation of COVID-19 symptoms is defined as all eight symptoms assessed by the subject as none (0) or mild (1) AND no single symptom reoccurs later at a level above mild (1).

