Note 2: Time to sustained alleviation is calculated as the number of hours from the first dose to the time of the occurrence of sustained symptoms alleviation. Subjects who did not

achieve sustained alleviation at the last assessment of the study are considered censored at the time of the last assessment.

Note 3: Percentiles and 95% CI of median are derived using the Kaplan-Meier method. P-values for treatment comparison are from Log Rank Test.

Source: Listing 16.2.6.1.2, 16.2.5.3

O:\Studies\EmitBio\EB-P12-01\Biometrics\Programs\Tables\xxx.sas ran on Month Day, Year at hh:mm on data from Month Day, Year.

Figure 15.3.1 - Kaplan-Meier Plot of Time to Sustained Alleviation of COVID-19 Symptoms for Intent-to-Treat Population

Figure 15.3.2 - Kaplan-Meier Plot of Time to Sustained Alleviation of COVID-19 Symptoms for Per-Protocol Population

Table 14.3.1.1 - Treatment-Emergent Adverse Events by System Organ Class and Preferred Term for Safety Population

System Organ Class Preferred Term	4 Days RD-X19 (N=XX) n (%)	7 Days RD-X19 (N=XX) n (%)	Sham (N=XX) n (%)
Subjects Reporting at Least One Adverse Event	XX (XX.X)	XX (XX.X)	XX (XX.X)
System Organ Class #1	XX (XX.X)	XX (XX.X)	XX (XX.X)
Preferred Term #1	XX (XX.X)	XX (XX.X)	XX (XX.X)
Preferred Term #2	XX (XX.X)	XX (XX.X)	XX (XX.X)
...			
System Organ Class #2	XX (XX.X)	XX (XX.X)	XX (XX.X)
Preferred Term #1	XX (XX.X)	XX (XX.X)	XX (XX.X)
Preferred Term #2	XX (XX.X)	XX (XX.X)	XX (XX.X)
...			

Counts reflect numbers of subjects reporting one or more TEAE that map to the MedDRA system organ class/preferred term. At each level of summarization (system organ class or preferred term), subjects reporting more than one TEAE are counted only once.

Source: Listing 16.2.7

O:\Studies\EmitBio\EB-P12-01\Biometrics\Programs\Tables\xxx.sas ran on Month Day, Year at hh:mm on data from Month Day, Year.

Table 14.3.1.2 - Treatment-Emergent Adverse Events by System Organ Class, Preferred Term and Severity for Safety Population

System Organ Class Preferred Term	Severity	4 Days RD-X19 (N=XX) n (%)	7 Days RD-X19 (N=XX) n (%)	Sham (N=XX) n (%)
Subjects Reporting at Least One Adverse Event	Mild	XX (XX.X)	XX (XX.X)	XX (XX.X)
	Moderate	XX (XX.X)	XX (XX.X)	XX (XX.X)
	Severe	XX (XX.X)	XX (XX.X)	XX (XX.X)
System Organ Class #1	Mild	XX (XX.X)	XX (XX.X)	XX (XX.X)
	Moderate	XX (XX.X)	XX (XX.X)	XX (XX.X)
	Severe	XX (XX.X)	XX (XX.X)	XX (XX.X)
Preferred Term #1	Mild	XX (XX.X)	XX (XX.X)	XX (XX.X)
	Moderate	XX (XX.X)	XX (XX.X)	XX (XX.X)

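### Subjects whose diary stops because COVID-19 worsened are censored like any other withdrawal in both time-to-alleviation endpoints, which partly hides a deficit in the arm that has them

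*Combined protocol and SAP*

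**What the plan says.** SAP 5.5.2 states that time to alleviation and time to sustained alleviation "will be derived from self-assessment by study subjects and recorded on" diary cards. Protocol 9.3.1 has subjects rate their "signs and symptoms of disease twice daily". The analysis is Kaplan-Meier with a log-rank p-value.

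The censoring rule is in Note 2 of each table. Table 14.2.5.1: "Subjects who did not achieve alleviation at the last assessment of study are considered censored at the time of the last assessment". Table 14.2.5.2 repeats it for those who did not "achieve sustained alleviation at the last assessment of the study are considered censored at the time of the last assessment".

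The protocol contains a path from clinical failure to an early end of the diary:

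- Section 9.1.1 says an unrecognised health problem "can lead to worsening of condition or hospitalization during study".
- Section 9.2.5 makes inpatient hospitalisation a serious adverse event.
- Section 8.5.3 lists "The occurrence of a SAE" among the reasons for which a subject may be removed.
- Section 8.5.4 says that when device use stops, "the study procedures for early termination should be completed as indicated by the Study Schedule of Activities". The schedule collects the diary at Day 8 or early termination.

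SAP 5.2.1 has a general sentence applying LOCF to missing efficacy data in the ITT analyses, whereas protocol 10.4 limits LOCF to viral load. Table 14.2.4 (severity score) carries an LOCF note. Tables 14.2.5.1 and 14.2.5.2 do not.

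**The concern.** Kaplan-Meier and log-rank methods assume that a censored subject would have gone on to alleviate at the same rate as those still followed. That is hard to defend for a subject whose diary stopped because the illness got worse, since the reason for censoring is then close to the opposite of the event.

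The plan has no non-recovery rule, no competing-event rule and no sensitivity analysis for this. The per-protocol repeat is no check, because SAP section 4 restricts that population to completers and so removes these subjects altogether.

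At stake are the medians, curves and log-rank p-values for two secondary endpoints. Both are also in the Cohort 1 interim tables, where the sham arm has only 10 subjects. The direction depends on which arm has the failures: failures on RD-X19 are understated in the device's favour, and failures on sham are understated against it.

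**Working it through.** **No plan figure to reproduce.** The documents give no power, effect size or event count for these endpoints, and SAP 3.2 calls the sample size one of convenience. The check compares two rules on the same data:

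- Rule A (SAP): censor at the last diary entry.
- Rule B: count the failed subject as not alleviated and keep the subject at risk to Day 8 (7 × 24 = 168 h).

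**Hand example (counts assumed).** Let n be the arm size, e1 the alleviations before the failures, r the failures (all on Day 3) and e2 the alleviations afterwards.

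Rule A = 1 − [(n − e1)/n] × [(n − e1 − r − e2)/(n − e1 − r)]. Rule B = (e1 + e2)/n.

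- Device, n = 20, e1 = 2, r = 3, e2 = 8: A = 1 − (18/20)(7/15) = 58%; B = 10/20 = 50%.
- Sham, n = 10, e1 = 1, r = 2, e2 = 4: A = 1 − (9/10)(3/7) = 61%; B = 5/10 = 50%.

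Timing matters. In the device example, if all 10 alleviations precede the failures, A = 1 − (10/20)(7/7) = 50% and the gap is zero. If all follow them, A = 1 − 7/17 = 59%. The example also assumes many failures (3/20 = 15% and 2/10 = 20%), so it shows the mechanism and not a likely size.

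**Simulation (inputs assumed).** Exponential time to alleviation with a 96 h median in both arms among subjects who do not fail; 12 h diary grid, from the twice-daily diary; last entry of failed subjects at 24 to 72 h; 20 RD-X19 against 10 sham, the Cohort 1 layout; 1,000 trials per scenario. Results are for the arm with the failures.

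| Arm, failures | Day 8 alleviated, A | Day 8 alleviated, B | Gap (points) | Typical median A / B (h) |
|---|---|---|---|---|
| 20, 1 | 0.700 | 0.671 | 2.9 | 96 / 96 |
| 20, 2 | 0.689 | 0.632 | 5.7 | 108 / 108 |
| 20, 3 | 0.678 | 0.593 | 8.5 | 108 / 120 |
| 20, 4 | 0.676 | 0.562 | 11.4 | 108 / 132 |
| 10 sham, 1 | 0.696 | 0.638 | 5.8 | 96 / 96 |
| 10 sham, 2 | 0.676 | 0.561 | 11.5 | 120 / 120 |

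Rule B agrees with direct arithmetic. Without failures the Day 8 proportion is 1 − 0.5^(168/96) = 0.703. Multiplying by 19/20, 16/20 and 9/10 gives 0.668, 0.562 and 0.633.

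With medians of 72 to 120 h, the gap for four failures in 20 runs from about 14 down to 10 points, and for one in 10 from about 7 down to 5.

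**Between-arm comparison.** With four device failures and none on sham, sham stands at 0.694. Rule B shows a device deficit of 0.694 − 0.562 = 13.2 points; Rule A shows 0.694 − 0.676 = 1.8 points. The mean log-rank z (positive favours the device) is −0.73 under B and −0.22 under A. With sham pooled to 20 it is −0.86 and −0.24. With one to four failures in the device arm only, A was more favourable to the device than B in essentially every simulated trial.

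**Sustained alleviation.** A subject who reaches none or mild, is then hospitalised and makes no further entries has no later entry above mild. As written, that subject counts as a sustained success.

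**The case against.** **Size and importance.** These are secondary endpoints in an unpowered, hypothesis-generating study, and SAP 5.1 makes the p-values descriptive. SAP 3.1 ties the choice of later dosing schedules to safety. The final tables use a single sham column, about 20 subjects, so the 10-subject figures apply to the interim only. Protocol 9.1.1 calls the risk of deterioration small, and the eligibility criteria exclude signs of respiratory distress. Removal under 8.5.3 is discretionary, and stopping the device does not by itself end study participation, so some worsening subjects may keep a diary to Day 8. All of this stands and limits the priority.

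**Estimand.** Counting a hospitalised subject as not recovered is a choice, because that subject could in principle be none or mild by Day 8. The Rule B figures are therefore a reference and not the truth. The choice is a standard one, and the plan makes none explicitly.

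**LOCF.** If the general sentence in SAP 5.2.1 covered the diary, a moderate or severe last entry would carry forward as not alleviated, close to the change proposed here. The table-specific notes and protocol 10.4 point the other way. This is an ambiguity to settle, not a safeguard.

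**Stronger readings.** A reader might infer that the arm with failures would look faster to recover than the other arm. The calculations do not support that: it stays slightly behind on average, with most of its deficit hidden. A reader might also infer, from the study population described as having "symptoms associated with COVID-19 that is either not under active medical treatment or is being treated as an outpatient", that outpatient COVID-19 treatment is allowed during the study and then counted as alleviation. Protocol section 7 describes the population at entry, so the text does not establish this.

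**Conclusion.** The point holds as a cheap improvement to the SAP. As written, both alleviation endpoints treat clinical failure as uninformative censoring, and no other part of the plan corrects for it. The affected arm's recovery is overstated relative to counting failures as not recovered.

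The size is conditional. One failure in 20 adds about 3 points at Day 8 and typically leaves the median unchanged. Four in 20 add about 11 to 12 points and move the typical median from 132 h to 108 h. One in 10 sham subjects at the interim adds about 6 points. These figures rest on an assumed 96 h median, exponential recovery and early failure. The primary viral-load analysis is unaffected.

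**What to change.** In SAP 5.5.2 and Note 2 of Tables 14.2.5.1 and 14.2.5.2, for the ITT analysis:

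1. A subject who dies, is hospitalised, or is discontinued with an SAE or AE of COVID-19 worsening, without having alleviated, is counted as not alleviated and stays at risk, censored at Day 8.
2. For sustained alleviation, the same applies if the failure comes after first reaching none or mild.
3. Other withdrawals keep last-entry censoring, and the present rule is reported as a sensitivity analysis.
4. The LOCF sentence in SAP 5.2.1 does not apply to these two endpoints.

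Failures should be identified from SAE, AE and disposition data before unblinding. For Cohort 1 that means before the interim, since the SAP lets the sponsor be unblinded there. Written criteria are needed, because Table 14.1.1 has no discontinuation category for COVID-19 worsening, and Clarification Memorandum 1 puts new COVID-19 symptoms through study day 3 on the diary and not on AE forms.

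The cost is SAP wording, modest programming and that short classification. The downside is slightly longer estimated times in an arm with failures. A supportive analysis of subjects who start other COVID-19 treatment is optional. Only the analysis changes; subject care does not.
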